### **2.7.2 Statistical hypothesis, model, and method of analysis**

No hypotheses will be tested for the secondary efficacy endpoints listed above and no p-values for the treatment comparisons will be provided.

### **2.7.3 Handling of missing values/censoring/discontinuations**

The summary is based on data with LOCF for missing data imputation.

For patients who are discharged from hospital before Day 29, biomarker data are not likely to be available after discharge.

## **2.8 Safety analyses**

There are no formal safety hypotheses in this study. All safety analyses will be descriptive and performed based on observed data using the safety set. According to the definition of the safety set, patients will be grouped by the actual treatment received.

The safety analyses will include all treatment-emergent data, i.e., data collected after the start of the study treatment up to the time of database cutoff date for the analyses based on Day 29 DBL or up to EoS for the final DBL after the end of the safety follow up at Day 127. A subset of outputs based on safety data in the first 29 days of treatment will also be created at the time of Day 29 DBL. The applicable outputs will be specified in TFL shell document.

### **2.8.1 Adverse events (AEs)**

A treatment-emergent adverse event (TEAE) is defined as any adverse event that develops on or after start of the study treatment or any event already present that worsens following exposure to the study treatment.

Adverse events will be coded using the MedDRA dictionary and presented by system organ class (SOC) and preferred term (PT). The MedDRA version used for reporting the study will be described in a footnote on AE related outputs.

The number (and percentage) of patients with TEAE will be summarized by treatment and presented by the SOCs in alphabetical order and the PTs in descending incidence in the canakinumab treatment arm. A patient with multiple adverse events within a given category is only counted once for summary purposes. AE, regardless of study drug relationship, will be summarized in the following ways:

- by treatment and preferred term
- by treatment, preferred term and maximum severity.
- by treatment, primary system organ class and preferred term.
- by treatment, primary system organ class, preferred term and maximum severity.

Summaries by primary system organ class and preferred term will be provided for serious adverse events.

In addition, AE (and SAE) suspected to be related to study medication, AE requiring additional therapy, AE requiring discontinuation of study treatment will be summarized by treatment, primary system organ class and preferred term

Serious AEs and study medication related AEs will be listed separately

### **2.8.1.1 Adverse events of special interest / grouping of AEs**

The number (and proportion) of patients with the adverse events that fulfill the risk search terms (listed below as defined in the case retrieval sheet) will be summarized by risk name, PT, and treatment:

- Infections
- Interactions with vaccines
- Opportunistic infections
- Drug induced liver injury
- Immunosuppressants combination therapy toxicity
- Macrophage activation syndrome

In the summary table, risk names will be sorted alphabetically and, within each risk name, the PTs will be sorted in descending order of frequency in the canakinumab arm. If a patient reported more than one adverse event with the same PT, the AE will be counted only once. If a patient reported more than one AE within the same risk, the patient will be counted only once at that risk.

SAEs of special interest, AEs of special interest suspected to be related to study treatment, and SAEs of special interest suspected to be related to study treatment, will also be summarized by risk name, PT and treatment group.

A list of the risk search terms used for the selection of AE of special interest will be provided.

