### **Potential risks due to study medication**

The risk to patients in this trial will be minimized by adherence to the eligibility criteria and close clinical monitoring, including by an internal DMC. Over 2,600 patients including approximately 480 children (aged 2 to 17 years) have been treated with canakinumab in interventional studies in Periodic fever syndromes, Still's disease, gouty arthritis, or other IL-1 beta mediated diseases, and healthy volunteers. The most frequently reported adverse drug reactions were infections, predominantly of the upper respiratory tract. The majority of the events were mild to moderate although serious infections were observed. No impact on the type

or frequency of adverse drug reactions was seen with longer-term treatment. Hypersensitivity reactions and opportunistic infections have been reported in patients treated with canakinumab. Neutropenia and leukopenia has also been observed with IL-1 inhibitors including canakinumab, with transient decreases to  $<1 \times 10^9$  /L observed during clinical trials with canakinumab.

In addition to experience in approved indications, over 10,000 patients were enrolled in the CANTOS study evaluating canakinumab for the prevention of recurrent cardiovascular events among stable post-myocardial infarction patients with elevated CRP, with a cumulative exposure of 32662.6 patient-years (21745.1 patient-years for total canakinumab and 10917.5 patient-years total for placebo).

No clinically meaningful differences between canakinumab and placebo were observed for most safety topics of interest, apart from an increase in serious infections and of fatal infections/sepsis; however, the overall incidence was low. The pattern of infections was stable over time, with very few confirmed opportunistic infections distributed evenly across the treatment groups. There was no evidence of tuberculosis reactivation in canakinumab-treated patients.

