The overall incidences of investigator-reported infection AEs and discontinuations due to infection AEs were comparable across the treatment groups. For investigator-reported infection SAEs, there were numerical differences of 1-2% in the overall incidence for the canakinumab 300 mg and 150 mg groups compared with placebo. Similarly, a slightly higher percentage of patients discontinued due to an infection SAE in the canakinumab 300 mg and 150 mg groups than in the placebo group. The majority of infection AEs consisted of non-serious upper respiratory tract infections which showed no clinically meaningful differences across the treatment groups. Increases in the order of 1% with canakinumab relative to placebo in the overall population were seen for certain infection events, i.e., sepsis, cellulitis, infectious pneumonias. The increase in cellulitis was seen predominately in patients with type-2 diabetes mellitus, and that of infectious pneumonias in patients with a history of asthma/chronic obstructive pulmonary disease. There was no meaningful difference between canakinumab 150 mg and 300 mg in the risk of cellulitis or infectious pneumonias; however, a higher risk of sepsis AEs with canakinumab 300 mg was observed.

Laboratory data showed an increase with canakinumab 300 mg only in mild neutrophil and platelet count abnormalities (Grade 1), with no imbalances in larger declines (Grades 2-4) in neutrophil and platelet counts, or in triglyceride levels, between 300 mg and 150 mg.

All-cause mortality was numerically lower across the three canakinumab treatment groups compared to placebo, with both fewer cardiovascular deaths and non-cardiovascular deaths. There was an increased incidence of deaths due to infection/sepsis for canakinumab 150 mg vs. placebo, although the numbers of related deaths were low overall.

The main adverse drug reaction was infection, of which the most common included viral upper respiratory tract infection, influenza, and pneumonia.

Overall, the safety and tolerability profile of canakinumab in post myocardial infarction patients was consistent with the known safety profile in the approved indications.

Known risks of canakinumab pertinent to short term use include the risks of infection (including opportunistic infection), interaction with live vaccines and the use in combination with other

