### 5.2 Exclusion criteria

Participants meeting any of the following criteria are **not** eligible for inclusion in this study.

1. History of hypersensitivity to canakinumab or to biologic drugs.
2. Intubated and on mechanical ventilation (invasive) at time of randomization
3. Treatment with immunomodulators or immunosuppressant drugs, including but not limited to tocilizumab, TNF inhibitors and anti-IL-17 agents within 5 half-lives or 30 days (whichever is longer) prior to randomization with the exception of anakinra which is excluded within 5 half-lives only. *Note: Immunomodulators (topical or inhaled) for asthma and atopic dermatitis and corticosteroids (any route of administration) are permitted*
4. Suspected or known untreated active bacterial, fungal, viral, or parasitic infection with the exception of COVID-19
5. Neutropenia with ANC  $< 1000/mm^3$
6. Any serious medical condition or abnormality of clinical laboratory tests that, in the investigator's judgment, precludes the patient's safe participation in and completion of the study
7. In the opinion of the investigator, progression to death is imminent and highly likely within the next 24 hours, irrespective of the provision of treatments
8. Current participation in any other investigational trials

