#### **9.1.1 Study treatment discontinuation and study discontinuation**

Discontinuation of study treatment for a participant occurs when study treatment is stopped earlier than the protocol planned duration and can be initiated by either the participant or the investigator.

The investigator must discontinue study treatment for a given participant if, he/she believes that continuation would negatively impact the participant's well-being.

Study treatment must be discontinued under the following circumstances

- Participant/guardian decision
- Use of prohibited treatment as per recommendations in the prohibited treatment section
- Any situation in which study participation might result in a safety risk to the participant
- Following emergency unblinding

- Emergence of adverse events that in the judgment of the investigator, taking into account the participant's overall status, prevent the participant from continuing participation in the study
- Any laboratory abnormalities that in the judgment of the investigator, taking into consideration the participant's overall status, prevents the participant from continuing participation in the study
- Severe hypersensitivity reaction occurs, including any of the following: anaphylaxis, fever, chills, urticaria, dyspnea, headache, myalgia, hypotension. Immediate interruption of the infusion to administer study treatment is required in such cases.

If discontinuation of study treatment occurs, the investigator should make a reasonable effort to understand the primary reason for the participant's premature discontinuation of study treatment and record this information.

Participants who discontinue study treatment or who decide they do not wish to participate in the study further should NOT be considered withdrawn from the study UNLESS they withdraw their consent (see 'Withdrawal of Informed Consent' section). **Where possible, they should return for the assessments indicated** in the Assessment Schedule. If they fail to return for these assessments for unknown reasons, every effort (e.g. telephone, e-mail, letter) should be made to contact the participant/pre-designated contact as specified in the lost to follow-up section. This contact should preferably be done according to the study visit schedule.

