#### **Adverse events**

The number (and percentage) of patients with treatment emergent adverse events (events started after the first dose of study medication or events present prior to start of double-blind treatment but increased in severity based on preferred term) will be summarized in the following ways:

- by treatment, primary system organ class and preferred term.
- by treatment, primary system organ class, preferred term and maximum severity.
- by treatment, Standardized MedDRA Query (SMQ) and preferred term.

A participant with multiple adverse events within a primary system organ class is only counted once towards the total of the primary system organ class.

Similar summaries will be provided for study medication related adverse events, death, serious adverse events.

The number (and proportion) of participants with adverse events of special interest/related to identified and potential risks (i.e. Infections, Opportunistic infections, Drug induced liver injury, Immunosuppressants combination therapy toxicity, Interactions with vaccines, Macrophage activation syndrome) will be summarized by treatment.

Deaths, serious AEs, and study medication related AEs will be listed separately.

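### The protocol's adverse event table by SMQ is missing from the SAP, and hypersensitivity is in no special-interest grouping, so no pooled count of hypersensitivity by arm is planned

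*SAP*

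**What the plan says.** **Hypersensitivity in the protocol.** Section 4.5 states: "Hypersensitivity reactions and opportunistic infections have been reported in patients treated with canakinumab". Section 5.2 excludes patients with "History of hypersensitivity to canakinumab or to biologic drugs". Section 9.1.1 requires study treatment to be discontinued, and the infusion interrupted at once, when a "Severe hypersensitivity reaction occurs, including any of the following: anaphylaxis, fever, chills, urticaria, dyspnea, headache, myalgia, hypotension".

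**Special-interest groupings.** Protocol 12.5.3 lists "Infections, Opportunistic infections, Drug induced liver injury, Immunosuppressants combination therapy toxicity, Interactions with vaccines, Macrophage activation syndrome". SAP 2.8.1.1 names the same six and counts "patients with the adverse events that fulfill the risk search terms (listed below as defined in the case retrieval sheet").

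**Adverse event tables.** Protocol 12.5.3 plans three breakdowns: by system organ class and preferred term, by those with maximum severity, and "by treatment, Standardized MedDRA Query (SMQ) and preferred term". SAP 2.8.1 lists four: by preferred term, by preferred term and severity, by system organ class and preferred term, and "by treatment, primary system organ class, preferred term and maximum severity". None uses SMQs.

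**Other relevant outputs.** SAP 2.8.1 also tabulates, by system organ class and preferred term, serious events, events suspected to be related to study medication, events requiring additional therapy and events requiring discontinuation of study treatment. SAP 2.4.1 counts, by arm, infusions interrupted for an adverse event and never restarted. SAP 2.8 adds a subset of outputs for the first 29 days.

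**The concern.** Hypersensitivity is an acute harm that the protocol takes seriously enough to exclude patients and stop treatment for. An acute reaction to an infusion is easiest to judge from one number per arm: how many patients had one, and how many soon after dosing. The plan does not produce that number. The protocol's SMQ table was the one planned output of a kind that could have pooled such terms, and the SAP omits it without a visible explanation.

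The signs listed in protocol 9.1.1 are a mixture of allergic, general, skin, respiratory, neurological, muscular and vascular terms. SAP 2.8.1 counts a patient once within a category, but no planned category brings these terms together. Several are also symptoms of the disease: protocol 1.1 gives fever and shortness of breath for COVID-19, and fever, headache and hypotension for CRS. The safety windows (data cut-off, first 29 days, end of study at Day 127) do not isolate the infusion day. A modest excess of reactions, especially ones that did not end the infusion, could thus be spread thinly over rows that already contain disease events.

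**Working it through.** The documents state no figure on this point, so the main check is a comparison of text.

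| Item | Protocol | SAP |
|---|---|---|
| Hypersensitivity as a reported harm | Yes (4.5) | Not addressed |
| Hypersensitivity as exclusion and stop criterion | Yes (5.2, 9.1.1) | Not addressed |
| Hypersensitivity among special-interest risks | No (12.5.3, six risks) | No (2.8.1.1, same six) |
| Table by SMQ and preferred term | Yes (12.5.3); SMQs not named | No (2.8.1) |
| Removal of SMQ table recorded | n/a | Not in the visible text of section 4 |
| Pooled count by arm that would include such reactions | None named | Only infusions stopped for any adverse event and never restarted (2.4.1) |

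Two things follow. The SMQ table is a departure of the SAP from the protocol. The special-interest omission is not; the SAP inherits it.

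**Does pooling help?** This is an illustration only, because every event rate is assumed. Inputs: 450/2 = 225 patients per arm (protocol 12.7.1); true hypersensitivity 4% on canakinumab (225 × 0.04 = 9 patients) against 0.5% on placebo (225 × 0.005 = 1.1); each reaction recorded as one of the eight listed signs at random. The mean excess per sign is 225 × (0.04 − 0.005)/8 = 0.98 patients. Visibility is proxied by a two-sided Fisher exact test at 0.05 with the excess on canakinumab. For a disease background b in both arms, the rate entering the count is 1 − (1 − h)(1 − b), where h is the hypersensitivity rate.

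| Count | Background b | Placebo vs canakinumab | Chance of p<0.05 |
|---|---|---|---|
| Pooled, Day 1-2 | 0% | 0.5% vs 4.0% | 64% |
| Pooled, Day 1-2 | 1% | 1.5% vs 5.0% | 45% |
| Pooled, Day 1-2 | 2% | 2.5% vs 5.9% | 36% |
| Pooled, Day 1-2 | 5% | 5.5% vs 8.8% | 22% |
| Pooled, Day 1-2 | 10% | 10.5% vs 13.6% | 14% |
| All eight signs pooled to Day 127 | about 20% | 20.5% vs 23.3% | 9% |
| Any of eight single rows to Day 127 | 1% to 5% per row | – | about 15% (about 7% with no harm) |

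The Day 127 background assumes 5% each for fever, dyspnea and hypotension, 3% for headache and 1% for each of the other four: 1 − 0.95³ × 0.97 × 0.99⁴ = 0.20.

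A second illustration isolates the effect of splitting. With 1% vs 5% in total and events divided evenly over independent terms, the pooled count reaches p<0.05 in 63% of trials. At least one of four terms does so in 15%, and at least one of eight in about 2%.

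So pooling helps when the pooled terms are specific or the window is clean. It fails, and can do worse than single rows, when nonspecific disease symptoms are pooled over the whole follow-up.

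**The case against.** **What stands against the point.** Protocol 10.1.1 asks for a diagnosis wherever possible in place of separate signs and symptoms. A recognised reaction should then appear under its own preferred term, and the assumption of one random sign per patient is pessimistic. Because protocol 9.1.1 makes severe hypersensitivity a reason to stop treatment, severe reactions during the infusion should reach the count in SAP 2.4.1. The suspected-related table filters out much of the disease background, since protocol 10.1.1 says events due to progression are usually judged not suspected. Safety is descriptive (SAP 2.8), so no table is judged at p<0.05.

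**Readings the documents do not support.** A reader might infer that an excess would be hidden, or that no patient count exists. Each term is shown by arm, and SAP 2.4.1 gives a pooled, if unspecific, count. A reader might infer that the SAP removed hypersensitivity from the special-interest list. It was never there, and protocol 4.5 also leaves it out of its own summary: "Known risks of canakinumab pertinent to short term use include the risks of infection (including opportunistic infection), interaction with live vaccines" and combination with other immunosuppressants. A reader might infer that the SMQ table would certainly have pooled hypersensitivity. The protocol names no SMQ. Finally, a reader might take the 64% as the detection power being lost. It needs no disease background at all on Days 1-2, which is implausible in hospitalized hypoxic patients.

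**What does not answer it.** The SAP 2.4.1 count mixes all adverse events and misses reactions after which the infusion was restarted and reactions starting after it ended. The other tables are again by system organ class and preferred term. The case retrieval sheet and the table shells are not available and part of SAP section 4 is redacted, so a grouping or an explanation may exist there. The SAP as visible commits to neither.

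**Conclusion.** The point holds in a limited form. One table planned in protocol 12.5.3 is absent from SAP 2.8.1 with no visible record. Separately, a harm that the protocol reports and treats as a stop criterion has no grouping in either document. The consequence is that no pooled patient count of hypersensitivity by arm is planned, so a modest excess could be diluted.

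The size is one missing table and one missing count in the safety reporting. No figure in the documents changes, and the efficacy analyses are untouched. The percentages above rest entirely on assumed rates. They support the direction of the argument and the design of the fix, but are no estimate of what the trial would miss. The conclusion also assumes that the unseen case retrieval sheet, table shells and redacted text do not already supply the grouping or the explanation.

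**What to change.** - In SAP 2.8.1, restore the table by treatment, SMQ and preferred term, and name the Hypersensitivity and Anaphylactic reaction SMQs.
- In SAP 2.8.1.1, add hypersensitivity as a grouping. Report patients by arm with onset on Day 1-2 and, separately, at any time, with the difference and 95% CI.
- Keep the nonspecific signs in protocol 9.1.1 (fever, dyspnea, headache, hypotension and the like) out of the main count. If wanted, show them in a separate Day 1-2 table.
- Say how imputed start dates enter the Day 1-2 count. Under SAP 5.1.2.2, an event that started in the treatment month with the day missing is generally placed on the day after treatment, which is Day 2.
- Record the change in SAP section 4. If the SMQ table was dropped on purpose, state the reason there.

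The cost is SAP wording and one or two more descriptive tables from adverse event data already coded in MedDRA. No patient procedure or treatment rule changes. The downside is that a Day 1-2 count will still catch some disease symptoms in both arms.

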## **10 Safety monitoring and reporting**

### **10.1 Definition of adverse events and reporting requirements**

#### **10.1.1 Adverse events**

An adverse event is any untoward medical occurrence (e.g. any unfavorable and unintended sign [including abnormal laboratory findings], symptom or disease) in a clinical investigation participant after providing written informed consent for participation in the study. Therefore, an AE may or may not be temporally or causally associated with the use of a medicinal (investigational) product.

The investigator has the responsibility for managing the safety of individual participant and identifying adverse events.

Novartis qualified medical personnel will be readily available to advise on trial related medical questions or problems.

The occurrence of adverse events must be sought by non-directive questioning of the participant at each visit during the study. Adverse events also may be detected when they are volunteered by the participant during or between visits or through physical examination findings, laboratory test findings, or other assessments.

Adverse events must be recorded under the signs, symptoms, or diagnosis associated with them, accompanied by the following information (as far as possible) (if the event is serious refer to [Section 10.1.2](#)):

1. Severity grade:
  - mild: usually transient in nature and generally not interfering with normal activities
  - moderate: sufficiently discomforting to interfere with normal activities
  - severe: prevents normal activities
2. Its relationship to the study treatment. If the event is due to lack of efficacy or progression of underlying illness (i.e. progression of the study indication) the assessment of causality will usually be 'Not suspected.' The rationale for this guidance is that the symptoms of a lack of efficacy or progression of underlying illness are not caused by the trial drug, they happen in spite of its administration and/or both lack of efficacy and progression of underlying disease can only be evaluated meaningfully by an analysis of cohorts, not on a single participant
3. Its duration (start and end dates) or if the event is ongoing, an outcome of not recovered/not resolved must be reported
4. Whether it constitutes a SAE (see [Section 10.1.2](#) for definition of SAE) and which seriousness criteria have been met
5. Action taken regarding with study treatment.

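### The SAP does not say whether COVID-19 terms fall in the 'Infections' risk; unless they are excluded, its patient count can dilute an excess of secondary infections

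*SAP*

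**What the plan says.** SAP 2.8.1.1 summarises patients with "adverse events that fulfill the risk search terms (listed below as defined in the case retrieval sheet". It names six risks, among them 'Infections' and, separately, 'Opportunistic infections'. At risk level, "If a patient reported more than one AE within the same risk, the patient will be counted only once at that risk". Below that, "within each risk name, the PTs will be sorted in descending order of frequency in the canakinumab arm". Companion tables cover serious events, "AEs of special interest suspected to be related to study treatment", and events that are both. The SAP adds: "A list of the risk search terms used for the selection of AE of special interest will be provided". Protocol 12.5.3 carries the same set of risks: "adverse events of special interest/related to identified and potential risks (i.e. Infections, Opportunistic infections".

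Four other places determine what can enter the 'Infections' row:

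- SAP 2.8.1 counts a condition present at dosing as treatment-emergent if it later gets worse. There is no exception for the study disease.
- Protocol 10.1.1 gives causality guidance for progression reported as an adverse event, beginning "If the event is due to lack of efficacy or progression of underlying illness (i.e. progression of the study indication". Causality is then usually recorded as not suspected. The same section prefers a diagnosis to a list of symptoms.
- Protocol 10.1.2 exempts hospital care for the indication from seriousness only when the patient has not deteriorated.
- Protocol 4.5 names infection as the main adverse drug reaction. It reports no clinically meaningful difference from placebo on most safety topics in the large cardiovascular trial, "apart from an increase in serious infections and of fatal infections/sepsis".

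**The concern.** The treatment is meant to reduce COVID-19 worsening, and infection is its main known harm. If both sit under one risk name with one count per patient, the row mixes an efficacy outcome with a safety outcome that may move the other way. A patient with worsening COVID-19 pneumonia and a patient with bacterial sepsis count the same. A patient with both adds nothing beyond the first event.

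SAP 2.8 plans no formal safety test, so these descriptive counts are what readers will use to judge infection risk. No visible AE or SAE output gives the number of patients per arm with an infection other than COVID-19.

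**Working it through.** **The plan's own figures.** The documents give no infection rate for this population and no figure for this table, so there is none to reproduce directly. The only relevant plan figure is the base of 450 patients randomised 1:1, or 225 per arm. With that base, a two-sided 5% comparison of 50% with 65% has 89.9% power, against 89% in SAP Table 3-1. The same function is used below purely as a yardstick for visibility.

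**Inputs, all assumed.** Let s be the proportion of an arm with a secondary infection and q the proportion with a COVID-19-term event. If the two are independent within an arm, the risk-level row shows

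pooled = 1 − (1 − s)(1 − q).

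**Case 1: s rises from 10% to 20%** (relative risk 2.00; 22.5 against 45 expected patients; nominal power 85% in a row without COVID-19 terms).

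| q placebo / canakinumab | Pooled row | Relative risk | Nominal power |
|---|---|---|---|
| 10% / 10% | 19% v 28% | 1.47 | 61.5% |
| 20% / 20% | 28% v 36% | 1.29 | 44% |
| 30% / 30% | 37% v 44% | 1.19 | 33% |
| 40% / 40% | 46% v 52% | 1.13 | 25% |
| 20% / 10% | 28% v 28% | 1.00 | none |
| 30% / 20% | 37% v 36% | 0.97 | reversed |

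The excess cancels when q in the canakinumab arm equals 1 − (1 − s0)(1 − q0)/(1 − s1), where 0 is placebo and 1 is canakinumab. For q0 = 20% this is 1 − 0.90 × 0.80/0.80 = 10%. For q0 = 30% it is about 21%, and for 40% it is 32.5%.

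**Case 2: s rises from 10% to 15%** (relative risk 1.5).

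- q = 20% in both arms: 1 − 0.80 × 0.90 = 28.0% against 1 − 0.80 × 0.85 = 32.0%, relative risk 1.14.
- q falls from 20% to 10%: 28.0% against 1 − 0.90 × 0.85 = 23.5%. A 5-point excess appears as a 4.5-point reduction.

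**Case 3: s rises from 5% to 10%.** With q = 20% in both arms, the row shows 24% against 28% (relative risk 1.17). With q falling from 20% to 10%, it shows 24% against 19%.

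**Case 4: an excess of the size in Protocol 4.5.** That section reports 1–2% differences in infection SAEs. With equal q, the pooled difference is (1 − q)(s1 − s0), so a 2-point excess shows as 0.80 × 2 = 1.6 points at q = 20%. For s of 5% against 7%, it cancels at q = 1 − 0.95 × 0.80/0.93 = 18.3%, a fall of only 1.7 points in COVID-19 reports.

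**Dependence.** If the same patients tend to have both events, masking can increase. Take q = 20% in both arms and full overlap, so that every patient with a secondary infection also has a COVID-19 report. Case 1 then shows 20% against 20%.

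**The case against.** A reader might infer that the plan counts every infection term and so hides secondary infections. The documents do not support that, for these reasons:

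- **The search terms are unseen.** They are in the case retrieval sheet, which may already leave COVID-19 terms out. The table shells are also unavailable, and parts of the SAP are blacked out. The SAP promises the term list with the outputs. This stands, and it makes the point conditional.
- **The same table has PT rows.** COVID-19 pneumonia and sepsis would appear on separate lines by arm, and SAP 2.8.1 adds further PT summaries and an SAE listing. This limits the point to the risk-level row. It does not remove it: secondary infections spread over many PTs, and one patient may appear in several, so the lines do not sum to patients.
- **The related-only tables would tend to drop progression reports.** They do give a patient-level count, but one that rests on case-by-case causality judgement. Protocol 10.1.1 itself says that progression can be evaluated meaningfully only in cohorts, not in a single participant.
- **Deaths are already separated.** SAP 2.8.1.2 tabulates fatal events by system organ class and PT, with a listing. This stands.
- **The known excess is modest.** Protocol 4.5 describes overall infection AE rates as comparable between groups. Cases 1 to 3 assume larger excesses, and reversal needs a drug effect on progression. Worsening might also be recorded under a respiratory diagnosis outside 'Infections', which would lower q.

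Nor is the count-once rule an error; it is standard practice. The gap is the missing statement about COVID-19 terms.

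**Conclusion.** The point holds as a conditional weakness in the safety reporting. The visible plan neither excludes nor separates COVID-19 terms, although worsening of the study disease is collected as a treatment-emergent event. If the retrieval sheet does not exclude those terms, the risk-level 'Infections' rows for AEs and serious AEs can dilute an excess of secondary infections. They can cancel or reverse it if the drug also lowers COVID-19 reports.

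With equal COVID-19 reporting of 10% to 40%, a true relative risk of 2.00 shows as 1.47 down to 1.13. Cancellation needs q to fall from 20% to 10%, from 30% to about 21%, or from 40% to 32.5%. These sizes depend on assumed rates and independence, and show what could happen rather than what is expected. No test or efficacy conclusion is affected. The change is worth making because it is cheap and gives a cleaner reading of the main known harm.

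**What to change.** In SAP 2.8.1.1:

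1. State whether COVID-19 terms are in the 'Infections' search.
2. For events of special interest and serious events of special interest, show three patient-level rows by arm: infections excluding a short list of COVID-19 PTs, COVID-19 terms, and the existing pooled row. Fix the list before unblinding.
3. Name the row excluding COVID-19 terms as the main reading of infection risk.
4. Show that row with and without unspecified 'pneumonia'. In this population such reports may often be the study disease, so placing them all on one side could bring the mixture back.

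No separate split of fatal events is needed.

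The cost is a short PT list, a few extra rows in tables already planned, and some terms that stay ambiguous. No data collection or efficacy analysis changes. The SAP's document history shows that liver safety criteria were revised in an amendment before the Day 29 database lock, so this is a familiar kind of edit. If the retrieval sheet already excludes COVID-19 terms, one sentence saying so resolves the main point.
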